Since there are no safety data for the medications to be evaluated on all arms of this study in the mild to moderate SARS-CoV-2 infected population, the first six patients on each arm will be evaluated for any grade 3 or higher hematologic or non-hematologic toxicity for 14 days. Patients coming off study before the first 14 days for reasons other than toxicity will be replaced. If two or more of the six patients in this arm of the study develop unacceptable toxicity, the treatment for that arm would be considered unsafe and stopped. Patients exhibiting rapid progression of COVID-19 symptomatology requiring intensive care hospitalization or intubation will come off study and will be considered failures in terms as per the primary endpoints of the study but nor for safety and will be replaced if these cases occurred during the phase 1 portion of the study.

Once the phase 1 portion safety run-in has concluded, that arm will be opened for phase II accrual.

Patients will be assigned to each arm in cohorts of three at a time until accrual numbers for each arm are fulfilled or discontinued due to safety concerns occurring beyond the Phase 1 portion. Monthly phone conferences among investigators during enrollment will take place.

Patients will undergo baseline mobile EKG or standard EKG to evaluate QTc interval on Day 1 (or within 5 days of registration if inpatient) and a repeat EKG at Day 14 (+/-4 days). Any Chest X-ray or CT scan of the chest that is performed for routine care will be reviewed by the PI for eligibility and recorded on case report forms. NOTE: if a patient develops a myocardial infarction or grade 3 or 4 cardiac arrhythmia while on the 14 days of drug, they should be immediately taken off study medication and receive standard of care treatment per their treating physician.

Patients will be followed for clinical outcomes by phone contact each week and hospitalizations, and all complications will be recorded on adverse event case report forms.

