## **6.2 Definition of Dose-Limiting Toxicity (DLT) for phase I run in portions of this protocol**

A DLT is defined as any of the below treatment emergent toxicities with attribution of definitely, probably or possibly related to one or more of the study drugs that occur during the first 14 days of study treatment. Toxicities that occur after the 14 day treatment period will be reported through adverse event reporting outlined in section 10.0, but will not be counted as DLTs.

- **Grade 3 or higher non-hematologic or non-hematologic toxicity at least possibly, probably or definitely related to study medication or procedures, per DMID Toxicity Scale for Determining Severity of Adverse Events**

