## **6.3 Duration of Therapy**

In the absence of treatment delays due to adverse event(s), treatment is given until one of the following criteria applies:

- Intercurrent illness that prevents further administration of treatment
- Unacceptable adverse event(s)
- Patient decides to withdraw from the study
- General or specific changes in the patient's condition render the patient unacceptable for further treatment in the judgment of the investigator
- Patient non-compliance
- Pregnancy
- The drug manufacturer can no longer provide the study agent
- Admission to the Intensive Care Unit and/or need for mechanical ventilation. At this

time, the treating physician will have the ability to continue study drug, discontinue therapy, place the patient on another study trial, or treat the patient with alternative therapies, per their clinical judgement. At this point, the patient will be followed by the study team to track outcomes and monitor for adverse events that might be attributable to study drug but the drug will be considered to have failed the primary endpoint

The reason(s) for protocol therapy discontinuation, the reason(s) for study removal, and the corresponding dates must be documented in the Case Report Form (CRF). For clarity, “off treatment” is the date when all medication has been completed (including the normal observation period) or discontinued due to one of the factors above, and no further treatment is planned. This is the date the patient has been officially taken off treatment. “Off study” is the date after which no further follow-up of the patient will occur

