#### **10.4 Exceptions to AE reporting**

Adverse events related to SARS-CoV-2 infection are exempt from adverse event reporting unless the investigator considers the event to be possibly, probably, or definitely related to the study drug or study procedures. Examples of COVID-19 related AEs include:

- Death not related to the study procedures
- Neurological events
  - Seizure
- Cardiovascular events
  - Atrial or ventricular arrhythmia
  - Cardiac arrest
- Respiratory events
  - Hypoxemia requiring supplemental oxygen
  - Acute respiratory distress syndrome
  - Receipt of mechanical ventilation
  - Receipt of extra-corporeal membrane oxygenation

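### Section 6.1 replaces run-in patients who progress to ICU care or intubation without an attribution step, so progression judged possibly drug-related is a DLT under 6.2 but uncounted under 6.1

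*Combined protocol and SAP*

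**What the plan says.** Section 6.1 (Agent Administration) sets up the run-in: "the first six patients on each arm will be evaluated for any grade 3 or higher hematologic or non-hematologic toxicity for 14 days". Its stopping rule begins "If two or more of the six patients in this arm of the study develop unacceptable toxicity", in which case the arm's treatment is considered unsafe and stopped. Section 9.1 states the same limit in terms of DLTs: 2 of the first 5, or at least 2 of 6.

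Section 6.1 then makes an exception: "Patients exhibiting rapid progression of COVID-19 symptomatology requiring intensive care hospitalization or intubation will come off study". These patients "will be considered failures in terms as per the primary endpoints of the study but nor for safety and will be replaced" when this happens in the phase 1 portion. The exception carries no relatedness condition.

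Section 6.2 defines DLTs as grade 3 or higher "treatment emergent toxicities with attribution of definitely, probably or possibly related to one or more of the study drugs" within the first 14 days of treatment. It makes no exception for disease progression.

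Section 10.4 exempts events related to the infection from adverse event reporting, with ARDS and mechanical ventilation among its examples, "unless the investigator considers the event to be possibly, probably, or definitely related to the study drug or study procedures".

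Section 6.3 says that after ICU admission or ventilation the study team goes on following the patient to track outcomes and "monitor for adverse events that might be attributable to study drug". It also defines the off-study date as the date after which follow-up ends.

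**The concern.** The run-in exists because, as 6.1 says, there are no safety data for these agents in mild to moderate infection. Section 2.6 leaves toxicity assessment to the run-ins and describes the Bayesian monitoring as an efficacy assessment. Faster or more severe progression is one form that drug harm could take in this population, and investigators may not always be able to rule out a drug contribution.

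For a patient in whom that contribution is judged possible, the two sections give opposite instructions. The limit is two patients, so a single reclassified patient is half of the stopping count. Whoever applies the rule can reach a different decision on whether the arm opens, depending on which section is read. Section 9.1 rules out comparison between arms or with placebo, so no control group would reveal an excess of progression.

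**Working it through.** **1. Is the conflict real for a single patient?** Take a run-in patient intubated on Day 6 with ARDS judged possibly related to study drug.

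| Question | Section | Answer |
|---|---|---|
| Is the grade at least 3? | Appendix G | Yes: ARDS with intubation indicated is grade 4 |
| Is it within 14 days and at least possibly related? | 6.2 | Yes, so it is a DLT |
| Does it count toward the stop? | 9.1 | Yes |
| Does it count for safety in the run-in? | 6.1 | No; the patient is replaced |
| Is it exempt from AE reporting? | 10.4 | No, because it is possibly related |

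If the same event is judged unlikely or unrelated, it is not a DLT under 6.2 either, and the sections agree. The conflict is therefore limited to progression judged at least possibly related.

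**2. What does it do to the run-in rule?** The plan gives no operating characteristic for the run-in, so there is no stated figure to reproduce. Define, per patient:

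- a = probability of another related DLT
- b = probability of ICU or intubation progression judged at least possibly related
- c = probability of such progression judged unrelated

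The documents give none of these; all three are assumptions. For c, a rough value comes from the 20% deterioration rate in 9.3 and the 20–30% of hospitalized patients needing intensive care in 2.1: 0.20 × 0.20 = 4% to 0.20 × 0.30 = 6%.

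Replaced patients drop out of the denominator, so the chance that one of the six counted patients has a DLT is:

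- 6.1 as written (all progressors replaced): p = a / (1 − b − c)
- 6.2 attribution (only unrelated progressors replaced): p = (a + b) / (1 − c)

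The chance that the arm stops is P(X ≥ 2) = 1 − (1 − p)^6 − 6p(1 − p)^5. The 2-of-first-5 clause does not alter this, since 2 of 5 is already at least 2 of 6.

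With a = 0 and c = 4%:

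| b | p under 6.1 | Stop under 6.1 | p under 6.2 | Stop under 6.2 |
|---|---|---|---|---|
| 10% | 0 | 0% | 0.10/0.96 = 0.104 | 12% |
| 20% | 0 | 0% | 0.20/0.96 = 0.208 | 37% |
| 30% | 0 | 0% | 0.30/0.96 = 0.3125 | 61% |

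The 0% follows by construction: if drug harm appears only as progression, no counted patient can have a DLT. With c = 6%, the last column becomes 13%, 38% and 62%.

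With a = 5% and c = 4%, 6.1 against 6.2 gives 4% against 24%, 5% against 49%, and 7% against 71% for b = 10%, 20% and 30%.

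**3. Would the harm show elsewhere?** The first futility look in 9.6 is after 10 randomized patients per arm, with a boundary of 7 or fewer stable, that is, 3 or more failures. Assume that replaced progressors stay in the m-ITT set as failures and that b adds to the 20% failure rate. The boundary is then met with probability 62%, 83% and 95% for b = 10%, 20% and 30%. At a 20% failure rate with no drug harm it is met 32% of the time.

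**4. Follow-up.** Section 6.1 takes these patients off study. Under 6.3's own definition that ends follow-up, yet 6.3 says the same patients are followed for attributable events. Both cannot hold.

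**The case against.** The strongest reply is that the exception is about disease, not toxicity. It covers only rapid progression of COVID-19, and just before it 6.1 replaces patients who leave for reasons other than toxicity. On that reading, calling an event progression already settles that the drug did not cause it. Keeping disease progression out of a small toxicity count is a defensible choice in a progressive infection. But the text does not say that the label settles causality. Section 10.4 treats events related to the infection as capable of being possibly drug-related, so the protocol itself recognises the overlap that 6.1 leaves unaddressed.

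Several stronger inferences are tempting, and the documents do not support them:

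- *That every ICU admission is removed.* The exception is limited to COVID-19 progression. Admission for, say, a drug-related arrhythmia is outside it.
- *That drug harm is hidden.* The same sentence makes these patients primary-endpoint failures. Section 10.3 requires expedited reporting of all drug-related grade 1–5 events in the run-in, 10.4 keeps possibly related events reportable, and the safety analysis in 9.5 includes everyone who received study drug.
- *That an arm could open and continue however many patients deteriorated.* Three such failures in the first ten meet the futility boundary. Four replaced patients plus six completers already make ten with at most six stable. The DSMC may suspend or terminate on safety grounds (13.3).
- *That different sites could reach different decisions.* The run-in decision is made once per arm, and patients are evaluated at one institution.

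These safeguards narrow the point but do not remove it. The futility look is an efficacy rule, and an arm with up to three replacements can complete its run-in by its ninth patient (6 + 3), before that look. Reporting an event does not restore it to the 2-of-6 count, and 13.3 does not list run-in replacements among the items that the DSMC monitors.

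**Conclusion.** The concern holds in a limited form. For ICU or intubation progression judged at least possibly drug-related, 6.1 and 6.2 give different DLT counts for the same patient, and the rule that opens an arm to phase II depends on that count. For progression judged unrelated there is no conflict. The separate conflict between 6.1 and 6.3 over follow-up also stands.

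The probabilities above illustrate the direction and possible scale; they are not estimates for this trial. They assume independent patients with a common risk and consistent attribution. How often the two sections would in fact lead to different decisions cannot be known from the documents. It should be corrected, because it affects the only rule in the plan designed to stop an arm for toxicity at the outset.

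**What to change.** Reconcile 6.1, 6.2, 6.3, 9.1 and 10.4 so that one stated attribution standard decides whether an ICU or intubation event in the run-in counts as a DLT or leads to replacement. State also whether the patient stays in follow-up. Sections 6.2 and 10.4 already share a threshold of at least possibly related; 6.1 is the section that has none. If the authors mean progression to stay outside the count even when possibly related, 6.2 and 9.1 need to say so and give the reason.

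Report to the DSMC, with each arm's run-in result and before that arm opens to phase II, the number of patients replaced for progression and the attribution given to each.

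The cost is a sentence or two in the affected sections and one line in the DSMC report. If 6.2 attribution is applied, the downside is that an arm may occasionally stop on an event that was in fact disease progression.

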## **6.2 Definition of Dose-Limiting Toxicity (DLT) for phase I run in portions of this protocol**

A DLT is defined as any of the below treatment emergent toxicities with attribution of definitely, probably or possibly related to one or more of the study drugs that occur during the first 14 days of study treatment. Toxicities that occur after the 14 day treatment period will be reported through adverse event reporting outlined in section 10.0, but will not be counted as DLTs.

- **Grade 3 or higher non-hematologic or non-hematologic toxicity at least possibly, probably or definitely related to study medication or procedures, per DMID Toxicity Scale for Determining Severity of Adverse Events**

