#### 4.9 Patient Registration to Treatment

To register a patient, the following information should be reviewed by the clinical research nurse (CRN) / clinical research associate (CRA) with the study physician per MCC SOPs to confirm eligibility:

- Copy of COVID19 testing results
- Mobile EKG tracing (outpatients) or standard EKG (inpatients) within 5 days of registration to assess QTc interval
- Eligibility labs, as well as correlative labs to be drawn
- Eligibility Checklist

Once eligibility is confirmed, the CRN/CRA will complete subject registration in the OnCore database (minimum data footprint) for randomization and complete study-required RedCap data forms. To complete the registration process, the CRN/CRA will:

- assign a patient study number
- register the patient on the study in OnCore
- receive the automated treatment arm assignment
- send an email or other communication to the study team of arm assignments.

If a patient is deemed ineligible for treatment their specimens will be retained in the COVID19 BIOBANK if the subject has indicated agreement to specimen collection and long-term storage in the consent form.

At the Day 1 visit or inpatient the following will be completed

- 1) Sign **treatment informed consent** (unless previously e-consented as above)
- 2) Undergo blood testing for eligibility (in subjects who have not had assessment of screening labs within the last 30 days will require blood draw)
- 3) Complete an eligibility questionnaire (age, concurrent diseases, current medications, contact information)
- 4) Undergo a mobile EKG or standard EKG tracing to assess QTc interval (within 5 days of registration)
- 5) Distribute medications, pill diary, and instructions
- 6) Baseline correlative blood sample
- 7) Sputum sample, with OP swab (alternative, if no sputum available)
- 8) Saliva sample
- 9) COVID-19 ordinal scale assessment (See Appendix B)
- 10) Limited visual physical exam unless a more complete exam is clinically indicated.

Day 3 or 4 phone call to assess clinical status and elicit concerns or questions.

Day 7 telehealth (+/- 4 days) is required for all patients to assess toxicity. If a subject has a standard of care telehealth visit during this period, this is also an acceptable toxicity assessment.

Day 10 or 11 phone call to assess clinical status and elicit concerns or questions

Day 14 (+/- 4 days) visit will also be completed in clinic or inpatient hospital.

- 1) Undergo blood testing for toxicity

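### The run-in DLT window closes at treatment Day 14, but the scheduled safety labs and EKG may come as late as Day 18, and no rule says how to date a finding first seen after Day 14

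*Combined protocol and SAP*

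**What the plan says.** **The window.** Section 6.2 defines a DLT as a related grade 3 or higher toxicity among those "that occur during the first 14 days of study treatment". Toxicities occurring after the 14-day period are reported under Section 10, "but will not be counted as DLTs".

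**The rule.** Section 6.1 states that "the first six patients on each arm will be evaluated for any grade 3 or higher hematologic or non-hematologic toxicity for 14 days", and stops the arm if two or more of the six have unacceptable toxicity. Section 9.1 states the same threshold in terms of DLTs. Section 6.1 then says: "Once the phase 1 portion safety run-in has concluded, that arm will be opened for phase II accrual".

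**The measurements.** Section 4.9 says "Day 14 (+/- 4 days) visit will also be completed in clinic or inpatient hospital". The first item listed for that visit is "Undergo blood testing for toxicity", and an EKG for QTc follows. Section 6.1 gives the repeat EKG the same +/- 4 day window. In the Section 11 calendar, CBC and CMP appear after Day 1 only at this visit, with a footnote that they are drawn if not obtained for routine care. The Day 28 EKG is only for routine-care indications. The contacts at Day 3 or 4, Day 7 and Day 10 or 11 are by phone or telehealth, with no labs or EKG listed.

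**Dating.** Section 10 requires the investigator to evaluate each adverse event, and Section 10.2 lists a start date. Neither says how the start of a laboratory or EKG abnormality is to be set.

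**The concern.** The 2-of-6 rule is the only numerical safety criterion between the run-in and phase II accrual in each arm. It works on onset within 14 days, but the scheduled tests that reveal silent hematologic, hepatic or electrolyte toxicity may be done after those 14 days. When a first abnormal value comes from a Day 16 sample, the true onset is unknown: it lies somewhere between the last normal result, possibly baseline, and Day 16. If site staff enter the sample date as the start date, the event falls outside Section 6.2. If they judge that it began on treatment, it counts. Two patients with the same result and the same attribution could then be handled differently because of appointment timing or recording habit.

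Symptomatic toxicity is not at issue, because the remote contacts can pick it up. The gap is limited to findings that only a blood test or an EKG can show.

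**Working it through.** The plan states no target DLT rate and no operating characteristics for the 2-of-6 rule, so there is no figure to reproduce. The check compares the windows, then asks which arms are exposed.

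**1. Window overlap.** Permitted visit days: 14 - 4 = 10 to 14 + 4 = 18, which is 9 days. If dosing starts on calendar Day 1, treatment Day 14 is calendar Day 14, and Days 15-18 (4 of the 9) lie outside the DLT window. Section 4.10 allows up to 7 days from registration to first treatment, and Section 8.1.5 ships the Arm E product overnight to outpatients. If dosing starts *d* days after calendar Day 1, the days outside number max(0, 4 - *d*):

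| *d* | 0 | 1 | 2 | 3 | 4 or more |
|---|---|---|---|---|---|
| Visit days outside the DLT window | 4 | 3 | 2 | 1 | 0 |

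These are counts of permitted days, not forecasts of when visits happen.

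**2. Effect on the rule under sample dating.** If *k* of the six run-in patients have their only post-baseline tests after the window, at most 6 - *k* can add a finding from those tests. The rule needs 2, so the tests alone cannot trigger it when 6 - *k* < 2, that is *k* = 5 or 6. This is a ceiling; nothing in the documents suggests it is likely.

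**3. Which arms.** Section 8 lists toxicities without grade-specific rates.

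- Arm D (14 days of dosing): thrombocytopenia, hypokalemia and liver function abnormalities, each in the 1-10% group.
- Arm F (14 days of dosing): neutropenia and anemia, both above 10%.
- Arm C (last dose Day 2): LFT elevations 2%. Days 15-18 are 15 - 2 = 13 to 18 - 2 = 16 days after the last dose; with the stated 18-hour terminal half-life, 13 x 24 / 18 = about 17 half-lives. Even if every LFT elevation were grade 3 or higher, P(at least 2 of 6) = 1 - 0.98^6 - 6 x 0.02 x 0.98^5 = 1 - 0.8858 - 0.1085 = 0.006.
- Arm E: nausea only, which is symptomatic.
- QTc: monitored in every arm and graded in Appendix G, but Section 8 lists QT prolongation for no arm.

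The hematologic items assume that the DLT bullet in Section 6.2, which names non-hematologic toxicity twice, is meant to match Section 6.1, which names both kinds.

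**4. Illustration only.** Let *p* be the true DLT probability per patient and *m* the share of DLTs left uncounted. With q = p(1 - m), P(arm stopped) = 1 - (1 - q)^6 - 6q(1 - q)^5. The documents give neither *p* nor *m*; the values below are assumptions.

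| *p* | *m* = 0 | *m* = 0.25 | *m* = 0.50 |
|---|---|---|---|
| 0.2 | 0.345 | 0.224 | 0.114 |
| 0.3 | 0.580 | 0.406 | 0.224 |
| 0.4 | 0.767 | 0.580 | 0.345 |
| 0.5 | 0.891 | 0.726 | 0.466 |

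For example, *p* = 0.4 and *m* = 0.25 gives q = 0.3, and 1 - 0.1176 - 0.3025 = 0.580. The table shows how a six-patient rule responds to lost events. It does not estimate the loss in this trial.

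**The case against.** The strongest reply is that Section 6.2 excludes toxicities that *occur* after the period, not those *detected* after it. An investigator may properly judge that a Day 16 neutropenia began on treatment and count it. On that reading the two windows do not contradict each other: one governs onset, the other visit logistics. This stands, and it limits the point to an unwritten dating rule. It does not remove the point, because for a silent abnormality the sample date is often the only date available.

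Second, earlier labs may exist, since routine-care CBC and CMP results can replace the protocol draw. That is plausible for inpatients, but nothing requires such results or places them within the 14 days, and the footnote does not extend to the Day 14 EKG.

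Third, Section 6.1 can fairly be read as requiring the toxicity bloods before the run-in is concluded, since it requires hematologic toxicity to be evaluated. That is the sensible reading, but it is implied rather than stated.

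Fourth, there are backstops. During the run-in, Section 10.3 sends related events of grades 1-5 to the PI, IRB and DSMC in expedited fashion. The DSMC can suspend or terminate (Section 13.3). An arm can be "discontinued due to safety concerns occurring beyond the Phase 1 portion" (Section 6.1), and Section 9.6 lets safety considerations drive arm-dropping. A late finding is therefore seen and can be acted on, although none of these routes applies the 2-of-6 count.

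A reader might infer that four ninths of DLTs would be lost. The documents do not support that: it would need visits spread evenly over Days 10-18, dosing from calendar Day 1, every DLT visible only at that visit, and every finding dated by its sample. Nor do they support saying that late-detected findings are excluded outright, or that QTc prolongation is an expected toxicity here.

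**Conclusion.** The point holds as a gap in the DLT definition. A related grade 3 or higher finding visible only on labs or EKG and first seen on Days 15-18 would be left out of the 2-of-6 rule if dated by its sample, even though it may have begun on treatment, and the protocol does not say which date to use. At most 4 of the 9 permitted visit days are affected, and fewer if dosing starts after calendar Day 1. The exposure lies mainly in Arms D and F. The effect on the chance of stopping an arm cannot be derived, because visit timing, true DLT rates and the share of lab-only events are not given. Severity is minor to moderate: the rule decides whether an arm proceeds, but expedited reporting and DSMC authority would bring a late finding to attention.

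**What to change.** Keep the Day 10-18 sampling window. Add to Section 6.2, with matching wording in Section 6.1:

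*For run-in patients, a related grade 3 or higher finding on any post-baseline CBC, CMP or EKG obtained up to and including the Day 14 (+/- 4 days) visit, whether drawn per protocol or for routine care, counts as a DLT unless earlier results show that it began after the 14-day treatment period. Phase II accrual in the arm opens only after these results have been reviewed for all six evaluable run-in patients.*

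No new visit or test is needed. Naming routine-care results matters because they may replace the scheduled draw. The cost is that a few abnormalities that truly began after treatment may be counted; that errs on the safe side and is limited by the relatedness requirement, which matters most in Arm C. The run-in decision may also come a few days later: up to 18 - 14 = 4 days for sampling if dosing starts on calendar Day 1, plus the time to review results.
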